6.4. Study Intervention Compliance

Study intervention will be administered under medical supervision by the investigator or designee. The dose of study intervention and study participant identification will be confirmed prior to the time of dosing. The date and time of each dose administered will be recorded in the source documents and in the CRF.

Any infusion at which 75% or more of the infusion solution is given will be considered a complete infusion. If a participant attends a visit but does not receive a complete infusion (for example, due to technical complications), every effort should be made to complete the infusion within 24 hours of preparation. If less than 75% of the infusion solution is given, this must be recorded as an incomplete infusion on the CRF.

Missed infusions should be recorded on the CRF. If at any time it is discovered that the participant has not completed proper dosing during the titration phase, the sponsor should be contacted prior to the subsequent infusions to discuss the possibility of completing a proper titration phase, if needed.

6.5. Dose Modification

Dose modification of donanemab is not permitted in this study except for participants whose amyloid plaque reduction meets criteria, as described in Section 4.1, and some instances of ARIA; if ARIA occurs during the titration period (that is, before the fourth infusion of donanemab), dose modification can be considered at the discretion of the investigator or designee as described in the Manual of Operations. If an ARIA-E and/or symptomatic ARIA-H event occurs, additional data should be provided to the sponsor in the ARIA Related Events CRF.

Investigators should consult the aducanumab appropriate product label/institutional guidelines toxicity management and dose modifications.

6.6. Continued Access to Study Intervention after the End of the Study

Not applicable.

6.7. Treatment of Overdose

In the event of an overdose, the investigator or treating physician should:

1. Contact the medical monitor immediately.
2. Evaluate the participant to determine, in consultation with the medical monitor, whether study intervention should be interrupted or whether the dose should be reduced.
3. Closely monitor the participant for any AE/SAE.
4. Obtain a plasma sample for analysis of study intervention if requested by the medical monitor (determined on a case-by-case basis).

Decisions regarding dose interruptions or modifications will be made by the investigator in consultation with the medical monitor based on the clinical evaluation of the participant.

6.8. Concomitant Therapy

Any medication or vaccine (including over-the-counter or prescription medicines, vitamins, and/or herbal supplements) that the participant is receiving at the time of enrollment or receives during the study must be recorded along with

- reason for use
- dates of administration including start and end dates, and

- dosage information including dose and frequency.

The medical monitor should be contacted if there are any questions regarding concomitant or prior therapy.

6.8.1. Medications for Alzheimer's Disease

Use of approved or standard of care symptomatic treatments for AD is permitted during the study. When medically indicated, initiation, increase, or discontinuation of symptomatic treatments for AD is permitted.

Disease-modifying prescription medications are not allowed at any time during the study.

Nonmedication treatments for AD, such as behavioral management, are permitted.

6.8.2. Medications for Infusion Reactions

If an infusion reaction occurs, medications managing the reaction may be administered at the discretion of the investigator or designee, according to local practice guidelines. If the need for concomitant medication arises, inclusion or continuation of the participant may be at the discretion of the investigator or designee. Concomitant therapy administered to treat an infusion reaction or as premedication for infusions should be documented in addition to completion of the Hypersensitivity, Anaphylactic, and Infusion-Related Reactions CRF.

6.8.3. Excluded Medications

IgG therapy (also known as gamma globulin or IVIG) is not allowed during the study. Use of medications with platelet anti-aggregant or anti-coagulant properties (unless aspirin at ≤ 325 mg daily) are not allowed during the study.

7. Discontinuation of Study Intervention and Participant Discontinuation/Withdrawal

Discontinuation of specific sites or of the study as a whole are handled as part of Appendix 1.

7.1. Discontinuation of Study Intervention

In rare instances, it may be necessary for a participant to permanently discontinue study intervention. If study intervention is permanently discontinued, the participant should remain in the study to be evaluated for safety and biomarker collection. See the SoA for data to be collected at the time of discontinuation of study intervention and follow-up and for any further evaluations that need to be completed.

A participant should be permanently discontinued from study intervention if

- the participant becomes pregnant during the study
- by request of the participant or participant's designee (for example, legal guardian)
- based on a specific AE profile, the Medical Monitor, or the study sponsor physician/scientist, in discussions with the Principal Investigator
- incorrect enrollment
- severe noncompliance to the study protocol in the judgment of the investigator
- systemic hypersensitivity reaction suspicious for an anaphylactic reaction or angioedema
- participant requires an excluded therapeutic agent
- based on investigator clinical judgment
- participants answered 'yes' to Question 4 or 5 on the 'Suicidal Ideation' portion of the C-SSRS, or
- participants answered 'yes' to any of the suicide-related behaviors on the Suicidal Behavior portion of the C-SSRS.
 - a psychiatrist or appropriately trained professional may assist in the decision to discontinue the participant for C-SSRS responses.

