6.1. Study Intervention(s) Administered

Intervention Name	donanemab	aducanumab
Dosage Level(s)	700 mg IV Q4W for first 3 doses and then 1400 mg IV Q4W ^a	refer to PI/routine clinical practice
Route of Administration	IV infusion	IV infusion
Use	experimental	active-comparator

Abbreviations: IV = intravenous; PET = positron emission tomography; PI = package insert; Q4W = once every 4 weeks.

^a Participants randomized to donanemab whose amyloid plaque reduction as measured by florbetapir F18 PET scans at Visit 8 (Week 24) or Visit 15 (Week 52) meets criteria will stop donanemab infusions but continue all other assessments for the remaining duration of the open-label period and short-term follow-up period. These dose reduction rules are defined by the sponsor.

Donanemab is administered by IV infusion over a minimum of 30 minutes. Detailed instructions for administration, including reconstitution and infusion rate, can be found in the pharmacy manual.

Donanemab is to be administered once Q4W. Donanemab must not be administered at a dosing interval of <21 days at any time in the study.

See Section 8.3.3.1 for infusion-related reactions.

For aducanumab, it is expected that the investigator review appropriate product label/institutional guidelines for confirmation dosing (i.e., need for pre-medication, dose, schedule, toxicity management and dose modifications).

Resuscitation equipment and rescue medications must be available wherever study intervention is administered.

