8.3. Adverse Events, Serious Adverse Events, and Product Complaints

The definitions of the following events can be found in Appendix 3:

- AEs
- SAEs
- PCs

These events will be reported by the participant (or, when appropriate, by a caregiver, surrogate, or the participant's legally authorized representative).

The investigator and any qualified designees are responsible for detecting, documenting, and recording events that meet these definitions and remain responsible for following up events that

are serious, considered related to the study intervention or study procedures, or that caused the participant to discontinue the study intervention or study (see Section 6.8.3).

Care will be taken not to introduce bias when detecting events. Open-ended and non-leading verbal questioning of the participant is the preferred method to inquire about event occurrences.

After the initial report, the investigator is required to proactively follow each participant at subsequent visits/contacts. All SAEs and AEs of special interest (as defined in Section 8.3.4) will be followed until resolution, stabilization, the event is otherwise explained, or the participant is lost to follow-up (as defined in Section 7.3). For PCs, the investigator is responsible for ensuring that follow-up includes any supplemental investigations as indicated to elucidate the nature and/or causality. Further information on follow-up procedures is provided in Appendix 10.3.

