8.3.3. Hypersensitivity Including Infusion-Related Reactions

8.3.3.1. Management of Infusion-Related Reactions

If a systemic hypersensitivity reaction occurs, additional data describing each sign or symptom should be provided to the sponsor in the Hypersensitivity, Anaphylactic, and Infusion-Related Reactions CRF. Participants who experience a systemic hypersensitivity, should have vital signs collected.

Locations where study participants are receiving study intervention should have appropriately trained medical staff and appropriate resuscitation equipment and rescue measures. It is recommended that participants who experience a systemic hypersensitivity reaction be treated per the local standard of care.

If a participant experiences a systemic hypersensitivity reaction or infusion-related reaction either involving 2 or more organ systems (for example, mucocutaneous, respiratory, cardiovascular, or gastrointestinal systems), or that is severe, additional blood and urine samples should be collected as close to the event as possible, as described in Section 10.2.1. Tryptase and when applicable urine *N*-methylhistamine should be repeated in approximately 4 weeks (and prior to the next infusion, if applicable) to obtain post-event baseline. Laboratory results are provided to the sponsor via the central laboratory and are not needed for clinical management of the participant.

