8.3.3.2. Dosing Rechallenge and Premedication for Infusions

Donanemab

Premedication for dosing is not planned. Dosing rechallenge is contraindicated in participants that have experienced a suspected or possible anaphylactic reaction (for example, reaction involving 2 or more organ systems [for example, mucocutaneous, respiratory, cardiovascular, or gastrointestinal systems] occurring in close proximity to dosing), in a prior dose (Sampson et al. 2006). For infusion-related reactions which are not suspicious for anaphylaxis, at the investigator's discretion, the participant may continue to receive study intervention. The participant may be premedicated for subsequent doses at investigator's discretion and according to local practice guidelines. Any premedication given will be documented as a concomitant therapy (Section 6.8).

Aducanumab

Investigators should consult the product label and follow local practice.

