8.3.4. Adverse Events of Special Interest

Specific safety topics of interest for this study include, but are not limited to, the following:

- ARIA-E
- ARIA-H
- Hypersensitivity, immediate and non-immediate, including infusion-related reactions and anaphylaxis

The topics listed above, as well as other topics which may be subsequently determined by the sponsor, will be subject to enhanced surveillance activities. Additionally, the topics above will be analyzed for presentation in the Clinical Study Report in accordance with the SAP.

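### Protocol 7.1 directs a permanent stop after suspected angioedema, but the donanemab rechallenge text in 8.3.3.2 does not mention angioedema and does not point to 7.1

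*Protocol*

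**What the plan says.** Protocol 7.1 lists the conditions under which a participant should be taken off study intervention for good. One is a "systemic hypersensitivity reaction suspicious for an anaphylactic reaction or angioedema". The list applies to both arms.

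Protocol 8.3.3.2 covers dosing after a reaction. Its donanemab paragraph says "Dosing rechallenge is contraindicated in participants that have experienced a suspected or possible anaphylactic reaction", and gives as an example a reaction close to dosing that involves at least two organ systems. It then turns to milder events: "For infusion-related reactions which are not suspicious for anaphylaxis", the investigator has discretion and "the participant may continue to receive study intervention", with premedication if wanted. The aducanumab paragraph refers the investigator to the product label and local practice.

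Two other places deal with reactions at infusion. Protocol 6.1 says "See Section 8.3.3.1 for infusion-related reactions". Protocol 6.8.2, on medication for infusion reactions, leaves continuation to the investigator or designee when such medication is needed.

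**The concern.** An investigator deciding whether to give the next donanemab dose would naturally open the section titled for rechallenge. That section gives explicit permission to continue, on a condition that mentions anaphylaxis alone. For a reaction that the sponsor's own stopping rule names, the permission is looser than the rule, and nothing in the paragraph sends the reader to the rule.

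What is at stake is participant safety: a possible re-dose after a reaction that the sponsor judged serious enough to end treatment. No efficacy result depends on it.

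**Working it through.** No arithmetic applies. The check compares the two rules case by case and then traces the cross-references.

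**Case by case (donanemab).**

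| Reaction | 7.1 | 8.3.3.2 | Same answer? |
|---|---|---|---|
| Systemic, suspected or possible anaphylaxis | Stop | Rechallenge contraindicated | Yes |
| Systemic, suspicious for angioedema, second organ system involved, close to dosing | Stop | Rechallenge contraindicated (fits the example given) | Yes |
| Systemic, infusion-related, suspicious for angioedema, not judged possible anaphylaxis (for example, one organ system) | Stop | Investigator may continue | **No** |
| Infusion-related, suspicious for neither | This item not triggered | Investigator may continue | Yes |

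Only the third row differs.

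**Is the third row a real case?** The protocol treats angioedema as separate from anaphylaxis. Section 7.1 joins them with *or*, and 10.2.1 names each as a trigger for laboratory samples. Section 8.3.4 lists "Hypersensitivity, immediate and non-immediate, including infusion-related reactions and anaphylaxis", so infusion-related reactions fall within hypersensitivity. A systemic reaction can therefore be infusion-related and suspicious for angioedema without meeting the anaphylaxis description.

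**Force of the wording.** Section 7.1 uses *should*, not *must*. It is still a directive: the liver criteria in 7.1.1 ask only that stopping be considered, whereas 7.1 says that it should happen. Section 8.3.3.2 uses *may*.

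**Cross-references from the infusion-reaction text.**

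- 6.1 leads to 8.3.3.1.
- 8.3.3.1 leads to the laboratory tests: "additional blood and urine samples should be collected as close to the event as possible, as described in Section 10.2.1".
- 10.2.1 mentions suspected angioedema beside anaphylaxis, but only to trigger samples, and does not refer to 7.1.
- The donanemab paragraph of 8.3.3.2 leads to 6.8, for recording premedication.
- 6.8.2 contains no section reference.

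None of these reaches 7.1.

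**A separate slip.** In 8.3, the sentence on following up events, including those that led a "participant to discontinue the study intervention or study (see Section 6.8.3"), cites Section 6.8.3. That section is Excluded Medications. Discontinuation is the subject of Section 7.

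**The case against.** The strongest reply is that the two sections do not contradict each other. A permission does not override a stopping rule, 7.1 sits under the heading for discontinuation, and a site that stops dosing complies with both sections. This stands. A reader might infer that the protocol authorises re-dosing after suspected angioedema. It does not: the looser answer appears only when 8.3.3.2 is read without 7.1.

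The reply also narrows the case, and that stands too. Section 7.1 requires a systemic reaction, and the bar in 8.3.3.2 covers suspected or merely possible anaphylaxis. Angioedema with a second organ system involved is already covered. It would be wrong to infer that suspected angioedema in general is left open.

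A third argument concerns terms. The discretionary sentence speaks of infusion-related reactions, whereas 7.1 speaks of systemic hypersensitivity reactions, and 8.3.3.1 names the two side by side. SAP 4.7.2 searches for angioedema and for the infusion-related reaction term as separate items within one combined analysis, which does not show that the sponsor classes angioedema as an infusion-related reaction. This is fair, and the SAP search should not be leaned on. But 8.3.4 places infusion-related reactions inside hypersensitivity, so the terms overlap. If a site did keep them apart, the rechallenge text would give no answer on angioedema, and that also calls for a pointer to 7.1.

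Finally, there are safeguards. The opening of Section 8 tells sites to raise immediate safety concerns with the sponsor at once so that continuing or stopping can be settled. Section 8.3.4 provides enhanced surveillance, and 8.3.3.1 a dedicated CRF. These lower the risk but leave the wording of the rechallenge section as it is.

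**Conclusion.** The inconsistency is real and narrow. For a systemic, infusion-related reaction on donanemab that is suspicious for angioedema but does not meet the anaphylaxis description, 7.1 directs a permanent stop, and 8.3.3.2 read alone leaves continuation to the investigator. Section 7.1 governs when both are read.

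The conclusion assumes that such a reaction can be both systemic and infusion-related in the protocol's sense, which 8.3.4 supports, and that some investigators will consult 8.3.3.2 without 7.1, which the documents can neither show nor exclude.

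The case is likely to be uncommon, but that is a judgement. A reader might want an expected number of participants. The donanemab arm is about 100 (200 randomised 1:1), but the documents give no rate for this reaction, so any count would come from an assumed rate. Nor should anyone infer an effect on the trial's evidence: sample size, Type I error, the primary analysis and the planned safety summaries are unaffected. The point is worth correcting because it concerns participant safety and takes only a few words. It does not call for a stand-alone amendment.

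**What to change.** At the next planned amendment:

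- In 8.3.3.2 (Donanemab), add suspected angioedema to the reactions after which rechallenge is contraindicated. Limit the discretionary sentence to reactions suspicious for neither anaphylaxis nor angioedema, with a reference to Section 7.1.
- In 6.8.2, make the sentence on continuation subject to Section 7.1. Do the same in the aducanumab paragraph of 8.3.3.2, because 7.1 covers both arms.
- In 8.3, change the pointer for events leading to discontinuation from Section 6.8.3 to Section 7.

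The cost is a handful of wording edits. Protocol 10.1.1 requires IRB/IEC approval of amendments, so the edits should travel with other changes. Assessments, sample size and analysis stay as they are.

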7.1.1. Liver Chemistry Stopping Criteria

Participants who are discontinued from study intervention due to a hepatic event or liver test abnormality should have additional hepatic safety data collected via the CRF.

Discontinuation of the study intervention for abnormal liver tests **should be** considered by the investigator when a participant meets 1 of the following conditions after consultation with the sponsor-designated medical monitor:

- ALT or AST >8X ULN
- ALT or AST >5X ULN for more than 2 weeks
- ALT or AST >3X ULN and TBL >2X ULN or INR >1.5
- ALT or AST >3X ULN with the appearance of fatigue, nausea, vomiting, right upper-quadrant pain or tenderness, fever, rash, and/or eosinophilia (>5%)
- ALP >3X ULN

- ALP >2.5X ULN and TBL >2X ULN
- ALP >2.5X ULN with the appearance of fatigue, nausea, vomiting, right quadrant pain or tenderness, fever, rash, and/or eosinophilia (>5%)

7.1.2. QTc Stopping Criteria

If a clinically significant finding is identified (including, but not limited to changes from baseline in QT interval corrected using QTcF after enrollment, the investigator or qualified designee will determine if the participant can continue in the study and if any change in participant management is needed. This review of the ECG printed at the time of collection must be documented. Any new clinically relevant finding should be reported as an AE.

7.1.3. Amyloid-Related Imaging Abnormalities (ARIA)

The development of ARIA-E and/or ARIA-H (microhemorrhages and/or cSS) are expected events and occur more commonly on treatment with donanemab and aducanumab.

While most cases of ARIA-E are asymptomatic, serious cases have been reported. Available data for donanemab suggest serious cases are most likely to occur early in dosing, after the first, second, or third infusion. For aducanumab, enhanced clinical vigilance for ARIA is recommended during the first 8 doses of treatment, particularly during titration.

ARIA-E

For asymptomatic mild-to-moderate ARIA-E, study intervention may be continued and participants may be monitored with unscheduled MRIs at the investigator's discretion.

If a participant develops ARIA-E to an extent deemed clinically significant by the investigator or designee, such as symptomatic ARIA-E or severe ARIA-E on imaging, then the investigator or designee may consider withholding study intervention (see Manual of Operations for temporary discontinuation guidance). The participant should be monitored for improvement by MRI(s) (fluid attenuation inversion recovery and T2* gradient-recall echo). Symptoms should be monitored in participants with symptomatic ARIA-E. Upon resolution of ARIA-E on imaging and resolution of associated symptoms, reinitiating study intervention can be considered by the investigator or designee. If resolution is not observed, participants should be permanently discontinued from study intervention, but continue other study activities (see Manual of Operations for permanent discontinuation guidance).

If ARIA-E occurs during the titration period, dose modifications may be considered (see Manual of Operations).

In the event of a finding of ARIA-E on MRI, the investigator is to complete the ARIA Related Events CRF regarding the presence or absence of symptoms related to the ARIA-E, and ARIA-E should be reported as an AE in the AE CRF. Information regarding symptoms attributed to the ARIA-E event should be entered in the ARIA Related Events CRF and should not be reported as AEs.

ARIA-H

See Manual of Operations for temporary and permanent discontinuation guidance. For new or increased number or severity of asymptomatic ARIA-H, in some circumstances, study intervention may be temporarily discontinued and participants monitored for related symptoms

and with unscheduled MRIs at the investigator's discretion. In the case of symptomatic ARIA-H, the investigator or designee should monitor for changes in symptoms and may consider withholding study intervention. Upon stabilization of ARIA-H and resolution of associated symptoms, reinitiating study intervention can be considered. If stabilization of imaging findings and resolution of associated symptoms is not observed, participants should be permanently discontinued from study intervention, but continue other study activities.

In the event of symptomatic ARIA-H, the investigator is to complete the ARIA Related Events CRF regarding the symptoms related to the ARIA-H, and ARIA-H should be reported as an AE in the AE CRF. Information regarding symptoms attributed to the ARIA-H event should be entered in the ARIA Related Events CRF and should not be reported as AEs.

